4.2 METHOD OF TREATMENT ASSIGNMENT AND BLINDING

All patients in this study will have the opportunity to receive treatment with fenebrutinib at a dose of 200 mg PO BID. All patients, study site personnel, Sponsor agents, and Sponsor personnel will be unblinded to the treatment assignment of this study; however, the treatment assignment from the parent study will remain blinded until the parent study is unblinded.

4.3 STUDY TREATMENT

The investigational medicinal product (IMP) for this study is fenebrutinib.

4.3.1 Study Treatment Formulation, Packaging, and Handling

4.3.1.1 Fenebrutinib

Fenebrutinib will be supplied by the Sponsor as 50-mg tablets. Tablets will be supplied in bottles appropriately labeled for this study. Fenebrutinib tablets should be stored at room temperature. For information on the formulation and handling of fenebrutinib, see the pharmacy manual and the Fenebrutinib Investigator's Brochure.

4.3.1.2 Background Therapy: Standard-of-Care H₁-Antihistamines for Chronic Spontaneous Urticaria

Patients should maintain a stable dose of standard-of-care H₁-antihistamines for the first 12 weeks of the study (see Section 4.3.2.2 for details). Refer to the local prescribing information for the formulation, packaging, and handling of these medications.

4.3.2 Study Treatment Dosage, Administration, and Compliance

4.3.2.1 Fenebrutinib

The treatment regimen is summarized in Section 3.1. Patients will receive the first dose of fenebrutinib at the Day 1 study visit. Thereafter, fenebrutinib will be self-administered. Each dose, administered approximately every 12 hours (i.e., twice a day, morning and evening), will consist of four 50-mg tablets (i.e. eight tablets per day). Fenebrutinib may be taken with or without food. Patients should be instructed that a missed dose should not be taken with the next scheduled dose.

Fenebrutinib tablets will be dispensed on site every 4 weeks. For periods in which study site visits (for assessments) are scheduled > 4 weeks apart, patients will be expected to visit the site to receive allotment of study drug.

Sites will be responsible for pre-populating the bottle label with the dates when patients are scheduled to take study drug during that time period. Under the corresponding dates listed on the affixed label, patients will record the time (morning and evening) each dose is taken. Refer to [Appendix 6](#) for bottle and label configuration.

To assess patient compliance with study drug administration, patients will be directed to bring all empty and partially-filled bottles to each study visit. The number of tablets issued minus the number of tablets returned will be used to calculate the number of tablets taken. Dosing compliance will be documented in the source documents. If compliance is $\leq 80\%$, the investigator or designee should counsel the patient and ensure steps are taken to improve compliance.

Any dose modification should be noted on the Study Drug Administration electronic Case Report Form (eCRF). Cases of overdose, medication error, drug abuse, or drug misuse, along with any associated adverse events, should be reported as described in Section 5.4.4.

Guidelines for dosage modification and treatment interruption or discontinuation for patients who experience adverse events are provided in Section 5.1.2.

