3. STUDY DESIGN

3.1 DESCRIPTION OF THE STUDY

This is a Phase II, multicenter, OLE study to evaluate the long-term safety and efficacy of fenebrutinib in patients with CSU who have completed the treatment period in a fenebrutinib CSU parent study. Patients may enroll in this OLE study at any time after completing the treatment period of the parent study. Up to 165 patients from parent study GS39684 are expected to be enrolled globally.

Patients will receive open-label fenebrutinib at a dose of 200 mg PO BID. Treatment may continue until the end of the study (see Section 3.2).

Because some patients enrolling in this study may be receiving fenebrutinib for the first time (i.e., those patients randomly assigned to placebo in the parent study), all patients will be monitored at Weeks 4, 8, and 12. Thereafter, patients will be monitored approximately every 12 weeks (see Appendix 1).

Patients should maintain a stable dose of standard-of-care H₁-antihistamines (background therapy) for the first 12 weeks of the study. Discontinuation or reduction in the dose of standard-of-care H₁-antihistamines may be attempted at any time after the first 12 weeks, at the investigator's discretion (see Sections 4.3.2.2 and 4.4 for details on background and concomitant therapies).

Monitoring for safety and tolerability will continue throughout the study, including evaluation of clinical laboratory results and assessment of adverse events. Patients with

[figure not shown]
disease worsening, as determined by the investigator, should return to the clinic as soon as possible for an unscheduled visit. The investigator may also conduct an unscheduled visit to assess the patient's disease condition.

Patients who discontinue study treatment (see Sections 4.6.1 and 5.1.2.2) will be asked to return to the clinic for a safety follow-up visit approximately 4 weeks after the last dose of study drug. Patients who refuse to complete the safety follow-up period should return to the clinic for treatment discontinuation visit.

Details regarding assessments at the safety follow-up, treatment discontinuation, and unscheduled visits are provided in Appendix 1.

Figure 1 presents an overview of the study design. A schedule of activities is provided in Appendix 1.

Figure 1 Study Schema

BID = twice a day; BL = baseline; PO = by mouth.

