Appendix 1: Schedule of Activities (Cont.)

BID=twice a day; CRP=C-reactive protein; CSU=chronic spontaneous urticaria; eCRF=electronic case report form; LDH=lactate dehydrogenase; OLE=open-label extension; PK=pharmacokinetics; PRO=patient-reported outcome; PhyGA-LS=Physician's Global Assessment of Disease Control-Likert Scale; Q4W=every 4 weeks; SC=study completion; SFU=safety follow-up; TD=treatment discontinuation; UAS=Urticaria Activity Score;UAS7=Urticaria Activity Score over 7 days; UCT=Urticaria Control Test; UV=unscheduled visit.

Note: (x)=optional/as clinically indicated.

- ^a Fenebrutinib tablets will be dispensed on site every 4 weeks. For periods in which study site visits (for assessments) are scheduled > 4 weeks apart, patients will be expected to visit site to receive allotment of study drug.
- ^b All assessments on Day 1 are conducted prior to study drug administration unless otherwise specified. Activities that were performed at final visit of the parent study, if within 3 months prior to Day 1, should not be repeated.
- ^c Patients who refuse to complete the safety follow-up period should return to the clinic for a treatment discontinuation visit.
- ^d Patients who discontinue study treatment will be asked to return to the clinic for a safety follow-up visit approximately 4 weeks after the last dose of study drug (see Section 4.6.1).
- ^e Concomitant therapy consists of any medication (e.g., prescription drugs, over-the-counter drugs, vaccines, herbal or homeopathic remedies, nutritional supplements) used by a patient in addition to protocol-mandated treatment from entry into the extension study to the final visit of the extension study. All such medications, including standard-of-care H₁-antihistamines for CSU, should be reported to the investigator and recorded on the Concomitant Medications eCRF.
- ^f After informed consent has been obtained but prior to initiation of study drug, only serious adverse events caused by a protocol-mandated intervention should be reported. After initiation of study drug, all adverse events will be reported until 4 weeks after the final dose of study drug. After this period, the Sponsor should be notified if the investigator becomes aware of any serious adverse event that is believed to be related to prior study drug treatment (see Section 5.6).
- ^g Includes measurement of pulse rate and systolic and diastolic blood pressure while the patient is in a seated position for at least 5 minutes

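### The tablet count scores an unopened bottle left at home as fully taken, so the 80% counselling trigger can miss substantial non-adherence

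*Combined protocol and SAP*

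**What the plan says.** Section 4.3.2.1 (Fenebrutinib) sets the dose at four 50-mg tablets twice a day, self-administered after Day 1. On compliance it says that "patients will be directed to bring all empty and partially-filled bottles to each study visit", and then that "The number of tablets issued minus the number of tablets returned will be used to calculate the number of tablets taken". Compliance at or below 80% obliges the investigator or a designee to counsel the patient and see that it improves. On record keeping: "Dosing compliance will be documented in the source documents".

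The section gives no denominator for the percentage and no counting period. It does not mention unopened bottles or tablets that cannot be accounted for. It does have patients write the time of each morning and evening dose under pre-printed dates on the bottle label (see also Appendix 6), but does not link that record to the count.

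On timing, Appendix 1 footnote a says "Fenebrutinib tablets will be dispensed on site every 4 weeks". Where assessment visits are more than 4 weeks apart, Section 4.3.2.1 adds that "patients will be expected to visit the site to receive allotment of study drug". Section 3.1 says "all patients will be monitored at Weeks 4, 8, and 12", then about every 12 weeks. Appendix 1 places the later Year 1 visits at Days 168, 252 and 365.

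**The concern.** Under subtraction, any tablet that does not come back counts as swallowed. A missing tablet can therefore only push the figure up. The return instruction feeds that error: a full bottle is neither empty nor partly filled, so it is not on the list, although it is the plainest evidence of doses not taken. The patient need not break any rule for the figure to be wrong.

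What is at stake is the protocol's own adherence safeguard. In a long-term, self-administered study, the 80% trigger is the only stated prompt for a site to act on poor adherence. It works from a figure that can read 100% when a whole supply has not been opened.

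A second question is how often the count is made. The visits at which bottles come back are not defined, and the size of gap the trigger can catch depends strongly on that interval.

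**Working it through.** **Inputs.** Dose 200 mg twice daily, 50-mg tablets, trigger at 80% or below (Section 4.3.2.1). Dispensing every 4 weeks (Section 4.3.2.1; Appendix 1, footnote a). Visit days 84, 168, 252 and 365 (Appendix 1). Assumptions, because the documents are silent: tablets issued equal tablets scheduled, and each dispensing is a 28-day supply.

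**The plan's own figure.** 2 × 200/50 = 8 tablets a day, as stated. So 28 days = 224 tablets, 84 days = 672, and 113 days = 904.

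**1. Unreturned tablets.** Let *t* be true adherence and *r* the share of leftover tablets that come back. Then

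measured compliance = (issued − returned)/issued = 1 − (1 − *t*)*r*.

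At *t* = 50%: all leftovers returned gives 50%; half gives 1 − 0.5 × 0.5 = 75%; a quarter gives 87.5%; none gives 100%. The trigger is missed when *r* < 0.20/(1 − *t*), which is 40% at *t* = 50% and 67% at *t* = 70%.

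**2. An unopened bottle kept at home.** With *B* tablets in it, true adherence is at most 1 − *B*/issued, while measured compliance is 100% if nothing else is left over. Bottle size is not given, so a range is shown:

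| Unopened tablets *B* | True adherence at most, 28-day count (224) | True adherence at most, 84 days (672) | Measured |
|---|---|---|---|
| 56 (7 days) | 75.0% | 91.7% | 100% |
| 112 (14 days) | 50.0% | 83.3% | 100% |
| 224 (28 days) | 0% | 66.7% | 100% |

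Over 113 days, *B* = 224 gives at most 680/904 = 75.2%. The measured figure is wrong in every row. In the 84-day column, only the full 28-day supply is enough by itself to take true adherence below 80%.

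**3. The counting interval.** Here all bottles are assumed to come back. The longest complete gap within one counting period that stays above 80% is:

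| Counting period | Tablets missed to fire trigger | Longest gap that escapes | Score | One day more |
|---|---|---|---|---|
| 28 days | 45 of 224 (5.6 days) | 5 days | 23/28 = 82.1% | 22/28 = 78.6% |
| 84 days | 135 of 672 (16.9 days) | 16 days | 68/84 = 81.0% | 67/84 = 79.8% |
| 113 days (365 − 252) | 181 of 904 (22.6 days) | 22 days | 91/113 = 80.5% | 90/113 = 79.6% |

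With the ±14-day windows, the last interval can run from 85 to 141 days, and the escaping gap from 16 to 28 days. A 16-day gap inside one 28-day count would score 12/28 = 42.9%. If it straddles two such counts, at least 8 days fall in one of them (20/28 = 71.4%), so the trigger still fires. A straddling gap of up to 10 days, five on each side, could escape 4-weekly counts.

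**4. Which interval the text means.** Section 4.3.2.1 ties bottle return to study visits without qualification. Elsewhere in the section, visits for assessments are marked as such, which suggests the unqualified term may be wider. Against that, the pregnancy-test footnote in Appendix 1 describes monthly site attendance as falling between in-clinic study visits, which suggests it is narrower. Neither reading can be excluded. Up to Week 12 the two agree, because visits are 4-weekly anyway.

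**The case against.** The strongest reply is that other records would reveal the problem. Opened bottles carry a dated field for each dose, so a 16-day gap leaves 32 fields blank or falsified. The Drug Inventory Log (Section 4.3.3) must show drug dispensed and returned, so an attentive site could see that a bottle has not come back. A full bottle that is brought in would be deducted, since the formula does not restrict returned tablets to opened bottles. This stands in part: the protocol does not make detection impossible. But the label on an unopened bottle stays at home with it, the log gives the patient no instruction and does not change the formula, and nothing tells the site to reconcile either record with the count.

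The supply size is assumed, and the 67% against 100% example is an unfavourable case. That is so, which is why a range is shown. The direction of the error does not depend on it.

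A reader might infer more than the documents support:

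- **That counts are pooled over 12 to 16 weeks.** The text never says so, and patients attend every 4 weeks for drug. It is an ambiguity.
- **That non-adherence is hidden from the database.** Section 4.3.2.1 names only dose modifications for the study drug form, but that does not show nothing else is collected. Section 5.4.4 also requires medication errors and drug misuse to be recorded, which may capture some missed doses.
- **That the drug will look safer per unit of exposure, or that concentrations are distorted.** Section 6.4 plans descriptive safety summaries with no exposure-adjusted rate. Plasma concentrations are measured directly and the tablet count does not alter them.

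**Conclusion.** The point holds for the compliance figure and the trigger that depends on it. As written, Section 4.3.2.1 credits unreturned tablets as taken and does not ask for unopened bottles, so a patient who complies with the return instruction can be scored at 100% when true adherence is at most 67%. That figure assumes 28-day supplies, tablets issued equal to tablets scheduled, and one of three supplies left unopened. With smaller bottles the overstatement is smaller but in the same direction.

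The counting interval is unresolved. If dispensing attendances are not included, complete gaps of 16 days (84-day count) or 22 days (113-day count) escape after Week 12, against 5 days within one 4-weekly count. This part is conditional on that reading and does not apply to the first 12 weeks.

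The consequence is an adherence check that can fail to prompt the action the protocol intends. It is worth correcting, but it is not evidence of bias in the planned safety, efficacy or pharmacokinetic summaries.

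**What to change.** In Section 4.3.2.1:

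1. Direct patients to bring all bottles (empty, partly used and unopened) to every 4-weekly dispensing attendance.
2. Count at each attendance, and compute compliance per dispensing period against the tablets scheduled for that period, leaving out days on which drug was withheld by direction.
3. Record bottles that do not come back as unaccounted for, not as taken, and check the count against the dose times on the labels. The label is self-reported, so it serves as a cross-check and does not replace the count.
4. Apply the existing 80% trigger to that figure.

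The cost is a paragraph of protocol wording and a few minutes of counting at visits that already take place. Reported compliance may look slightly lower, because tablets that cannot be traced no longer count as taken.

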4.3.2.2 Background Therapy: Standard-of-Care H₁-Antihistamines for Chronic Spontaneous Urticaria

All patients will be permitted to take H₁-antihistamine medications consistent with standard of care during the study. Standard-of-care H₁-antihistamines should be reported to the investigator and recorded on the Concomitant Medications eCRF.

Patients should maintain a stable dose of standard-of-care H₁-antihistamines for the first 12 weeks of the study. Discontinuation or reduction in the dose of standard-of-care H₁-antihistamines may be attempted at any time after the first 12 weeks, at the investigator's discretion. If an attempt is unsuccessful, the medication may be returned to an effective dose at the discretion of the investigator. In addition, standard-of-care H₁-antihistamines may be added at any time during the study, at the investigator's discretion. Exacerbations of urticaria may be treated with standard-of-care medications (e.g., short course of systemic corticosteroids for up to 10 days) (Zuberbier et al. 2018).

4.3.3 Investigational Medicinal Product Accountability

All IMPs required for completion of this study will be provided by the Sponsor where required by local health authority regulations. The study site will acknowledge receipt of IMPs using an interactive voice or web-based response system to confirm the shipment condition and content. Any damaged shipments will be replaced.

IMPs will either be disposed of at the study site according to the study site's institutional standard operating procedure or be returned to the Sponsor (if supplied by the Sponsor) with the appropriate documentation. The site's method of destroying Sponsor-supplied IMPs must be agreed to by the Sponsor. The site must obtain written authorization from the Sponsor before any Sponsor-supplied IMP is destroyed, and IMP destruction must be documented on the appropriate form.

Accurate records of all IMPs received at, dispensed from, returned to, and disposed of by the study site should be recorded on the Drug Inventory Log.

4.3.4 Continued Access to Fenebrutinib

Currently, the Sponsor (Genentech, a member of the Roche Group) does not have any plans to provide Genentech IMP (fenebrutinib) or any other study treatments or interventions to patients who have completed or discontinued from the study. The Sponsor may evaluate whether to continue providing fenebrutinib in accordance with the Roche Global Policy on Continued Access to Investigational Medicinal Product, available at the following web site:

http://www.roche.com/policy_continued_access_to_investigational_medicines.pdf

4.4 CONCOMITANT THERAPY, PROHIBITED FOOD, AND ADDITIONAL RESTRICTIONS

Concomitant therapy consists of any medication (e.g., prescription drugs, over-the-counter drugs, vaccines, herbal or homeopathic remedies, nutritional supplements) used by a patient in addition to protocol-mandated treatment from entry into the extension study to the study completion/discontinuation visit of the extension study. All such medications, including standard-of-care H₁-antihistamines for CSU, should be reported to the investigator and recorded on the Concomitant Medications eCRF. The investigator should consult the prescribing information and contact the Medical Monitor (or delegate) if questions arise regarding concomitant medications not listed in the protocol.

4.4.1 Permitted Therapy

Patients are permitted to use the following therapies during the study:

- Hormone-replacement therapy or oral contraceptives
 - Hormone-replacement therapy or hormone contraceptives containing the CYP3A substrate ethinyl estradiol (with the concomitant use of a barrier method) is permitted. However, these agents should be used with caution as outlined in Section 4.4.2.3.
- Dietary supplements, defined as vitamins, minerals, purified food substances, and herbal therapies with pharmaceutical properties
 - Vitamins, minerals, and purified food substances are permitted in amounts lower than that known to be associated with adverse effects (e.g., hypervitaminosis). Herbal therapies with pharmaceutical properties are permitted only if there is acceptable evidence of no CYP3A inhibition or induction.

- Leukotriene receptor antagonists or H₂RAs for diseases other than CSU (e.g., asthma or gastroesophageal reflux disease, respectively) at a stable dose
- PPIs or H₂RAs at a stable dose, up to the maximum recommended dose according to the local prescribing information
- Inhaled asthma controllers, including inhaled corticosteroids

4.4.2 Cautionary Therapy

Categories of medications that are to be avoided or used with caution when combined with fenebrutinib are described below, and [Appendix 5](#) lists examples of medications within these categories. If use of one of these medications is necessary, the risks and benefits should be discussed with the Medical Monitor (or delegate) prior to concomitant administration with fenebrutinib.

4.4.2.1 Immunosuppressive Agents

Caution is advised if adding an immunosuppressive agent (e.g., methotrexate, mycophenolate mofetil, cyclophosphamide, rituximab, tacrolimus) to ongoing treatment with fenebrutinib.

4.4.2.2 Acid-Reducing Agents

Patients who use antacids for symptomatic relief of heartburn (e.g., Pepto-Bismol[®], Rolaids[®]) should take fenebrutinib at least 2 hours before or 2 hours after antacid administration because gastric acid improves fenebrutinib absorption.

4.4.2.3 Medications Given with Precaution due to Effects Related to Cytochrome P450 Enzymes

Preliminary data from the clinical drug–drug interaction study (GP39616), evaluating the effect of fenebrutinib on the pharmacokinetics of the sensitive CYP3A substrate midazolam, suggest that fenebrutinib can be classified as a mild inhibitor of CYP3A at clinically relevant doses. It is possible that fenebrutinib inhibition of CYP3A may alter the metabolism of CYP3A substrates and result in increased plasma concentrations of CYP3A substrates. Therefore, medications in the following categories should be used with caution and in consultation with the Medical Monitor (or delegate) as needed:

- Sensitive CYP3A substrates
- CYP3A substrates with a narrow therapeutic window

The use of hormone-replacement therapy or hormone contraceptives containing the CYP3A substrate ethinyl estradiol (with the concomitant use of a barrier method) is permitted. Ethinyl estradiol is metabolized by CYP3A (Wang et al. 2004; Zhang et al. 2007) so plasma concentrations of ethinyl estradiol are expected to increase in the presence of fenebrutinib. Ethinyl estradiol is not a sensitive substrate of CYP3A (FDA 2016). Therefore, the magnitude of increase in ethinyl estradiol plasma concentrations is expected to be less than the increase observed in midazolam concentrations (i.e., less than 2-fold) in Study GP39616. Minor increases in ethinyl

estradiol concentrations are not generally associated with adverse events (e.g., Ortho Tri-Cyclen[®] U.S. Package Insert). Ethinyl estradiol efficacy is expected to be maintained, and ethinyl estradiol continues to be considered a reliable and effective form of contraception in combination with fenebrutinib.

Preliminary data from Study GP39616 also suggest that fenebrutinib can be classified as a moderately sensitive substrate of CYP3A at clinically relevant doses. There is a moderate potential for a drug–drug interaction with any medication that strongly inhibits or induces this enzyme. Therefore, medications in the following categories should be avoided for 7 days or 5 drug-elimination half-lives, whichever is longer, prior to the first dose of fenebrutinib and during the treatment period (i.e., until the final dose of fenebrutinib):

- Strong CYP3A inhibitors
- Moderate or strong CYP3A inducers

4.4.2.4 Medications Given with Precaution due to Effects Related to Breast Cancer Resistance Protein

Preliminary data from Study GP39616 suggest that fenebrutinib is a moderate inhibitor of the breast cancer resistance protein (BCRP) (also known as ABCG2) at clinically relevant doses. Consequently, fenebrutinib may alter transport of BCRP substrates and result in increased plasma concentrations of BCRP substrates. Therefore, BCRP substrates with a narrow therapeutic window should be used with caution and in consultation with the Medical Monitor (or delegate) as needed:

4.4.2.5 Dose Adjustments for Statins due to Effects Related to Cytochrome P450 Enzymes or Breast Cancer Resistance Protein

Because several lipid-lowering agents (statins) are metabolized by CYP3A (simvastatin, lovastatin) and/or transported by BCRP (rosuvastatin, atorvastatin) and thus may be affected by drug–drug interaction with fenebrutinib, dose adjustments of these medications should be considered (Kellick et al. 2014), as outlined below:

- Simvastatin: recommended maximum dose of 10 mg/day
- Lovastatin: recommended maximum dose of 20 mg/day
- Rosuvastatin: recommended maximum dose of 10 mg/day
- Atorvastatin: recommended maximum dose of 20 mg/day

The use of statins has been associated with myopathy, which can manifest as weakness, tenderness, or muscle pain, with elevations of creatine kinase above 10× upper limit of normal (ULN). In severe cases, myopathy can cause rhabdomyolysis with or without acute kidney injury secondary to myoglobinuria, and rare fatalities due to rhabdomyolysis have occurred. The risk of myopathy is increased by elevated plasma levels of statins. Predisposing factors for myopathy include advanced age (≥65 years), female sex, uncontrolled hypothyroidism, renal impairment, or use of concomitant medications that increase the plasma levels of the statin.

